2.2 TREATMENT GROUPS

Treatment groups of the study consist of various dose level cohorts (starting at 10 mg twice daily (bid) for 21 days (a “Cycle”)) used in the dose-escalation phase of the study and the group number (Group 1 - Group 7 as specified in Section **Error! Reference source not found.**) used in the cohort expansion phase of the study and dosed at the RP2D.

2.3 STUDY ENDPOINTS

2.3.1 Primary Endpoints

Safety

- Evaluation of the DLTs of BVD-523
- Determination of MTD of BVD-523
- Determination of RP2D of BVD-523
- Evaluation of treatment-related AEs of BVD-523

2.3.2 Secondary Endpoints

Pharmacokinetics

- Evaluation of pharmacokinetic parameters of BVD-523 and selected metabolites in patients with advanced malignancies

Efficacy

- Preliminary clinical effects on tumor response assessed by physical or radiological exam (RECIST [Response Evaluation Criteria In Solid Tumors] version 1.1)

2.3.3 Exploratory Endpoints

Pharmacodynamics: Evaluation of multiple biomarkers to characterize response to drug (pRSK, pERK, Ki67, Caspase-3, and circulating tumor DNA). Additional biomarkers may be identified during the study and measured as appropriate. Tumor genotyping by DNA analysis will be performed to identify somatic alterations, relying on either available archived tissue or freshly-collected samples.

3 STUDY DESIGN

3.1 OVERALL STUDY DESIGN

This is an open-label, multi-center Phase 1 study to assess the safety, pharmacokinetics, and pharmacodynamics of escalating doses of BVD-523 in patients with advanced malignancies. It will be conducted at up to 15 sites. This clinical study comprises 2 parts: Part 1: Dose-escalation Phase and Part 2: Cohort Expansion Phase.

Part 1: Dose-escalation Phase, An accelerated dose escalation plan will be used to establish DLT, MTD, and the RP2D. One to 6 patients per treatment cohort will be assigned to receive sequentially higher oral doses of BVD-523 on a twice daily schedule (b.i.d.) for 21 days (a “Cycle”), starting at a dose of 10 mg twice daily. Patients will receive twice-daily oral doses of BVD-523 until disease progression, unacceptable toxicity, or a clinical observation satisfying another withdrawal criterion is noted. Treatment cycles will occur consecutively without interruption, except when necessary to manage toxicities. Up to 40 patients will be enrolled in Part 1. Patients with advanced-stage solid tumors only (no hematological malignancies) will be enrolled in the dose-escalation phase of the study. The study will initially be conducted as an accelerated single patient cohorts design, followed by a standard 3 + 3 design, informed by the accrued safety experience throughout the study (see Table 1 below). All dose-escalation decisions will be based on Cycle 1 safety data. Patients who withdraw at any time preceding the last visit of Cycle 1 (Day 22) will constitute an early discontinuation and must be replaced in order to ensure proper data accrual for dose escalation decisions. A patient who experiences a DLT in Course 1 and withdraws before Day 22 either because of the toxicity or otherwise, will nonetheless have that DLT counted in the assessment of potential cohort expansion and/or dose escalation. Doses will not be escalated unless the patient(s) receiving the highest current dose has been observed for at least 3 weeks. No intra-patient dose escalation was permitted under the original protocol or the first two amendments. Starting under amendment three, intra-patient dose escalations were allowed; see protocol for details.

Once the RP2D is defined, intra-patient dose escalation to the R2PD will be allowed after a patient has completed at least 1 cycle at their assigned dose and only if the patient has experienced no toxicity above Grade 1, upon request by the PI and discussion with the Medical Monitor and the Sponsor.

Table 1: Summary of Dose Escalation

Single Patient Cohorts	
Observed Safety Outcomes	Action
AEs \leq Gr 1	
 Continue testing with single patient cohorts Escalate by 100% to next dose level
One AE \geq Gr 2 (excluding alopecia or diarrhea)	
 Expand current and subsequent cohorts to \geq 3 patients Escalate by \leq 50% to next dose level
1 DLT	
 Expand cohort up to 6 patients
Standard Escalation Cohorts (3–6 patients)	
Observed Safety Outcomes	Action
No DLTs	
 Escalate by \leq 50% to next dose level
1 DLT in 3 patients	
 Expand cohort up to 6 patients
1 DLT in 6 patients	
 Escalate by \leq 50% to next dose level
$>$ 1 DLT in \leq 6 patients	
 Stop dose escalation

When more than 1 DLT occurs in \leq 6 patients in a dosing cohort, dose escalation will be stopped and this dose level will be identified as a non-tolerated dose. Doses between the non-tolerated dose and the preceding lower dose, where \leq 1 DLT occurred, may be explored to define the MTD.

In Part 2 – Cohort-expansion Phase, an additional (approximately 105) patients with particular tumor types and/or cancers harboring specific genetic mutations (as specified in patient groups 1-7 below) will be recruited for treatment at the RP2D. Patients must have measurable disease by RECIST 1.1. Patients will receive twice daily oral doses of BVD-523 in 21-day treatment cycles until disease progression, unacceptable toxicity, or another withdrawal criterion is met. Treatment cycles will occur consecutively without interruption except when necessary to manage toxicities. Intra-patient dose modifications are allowed, including dose reductions/interruptions as needed and re-escalations up to and including RP2D, at Clinical Investigator’s discretion.

- Group 1: Patients with BRAF mutated cancer, except those with colorectal or non-small cell lung cancers, not previously treated with BRAF and/or MEK inhibitors; $n \leq 15$
- Group 2: Patients with BRAF mutated colorectal cancer, not previously treated with BRAF and/or MEK inhibitors; $n \leq 15$
- Group 3: Patients with BRAF mutated melanoma who have progressed or are refractory to BRAF and/or MEK inhibitors; $n \leq 15$
- Group 4: Patients with NRAS mutated melanoma; not previously treated with BRAF and/or MEK inhibitors; $n \leq 15$
- Group 5: Patients with MEK mutated cancer, not previously treated with BRAF and/or MEK inhibitors; $n \leq 15$

- Group 6: Patients with BRAF mutated non-small cell lung cancer, not previously treated with BRAF and/or MEK inhibitors; $n \leq 15$
- Group 7: Patients with ERK mutated cancer, not previously treated with BRAF and/or MEK inhibitors; $n < 15$

It is agreed that for reasonable cause, either the investigator or the Sponsor may terminate this study, provided a written notice is submitted at a reasonable time in advance of intended termination; if by the investigator notice is to be submitted to BioMed Valley Discoveries, Inc., and if by the Sponsor, notice will be provided to each investigator.

If a severe local reaction or drug-related serious adverse event (SAE) occurs at any time during the study, the Safety Monitoring Committee (SMC) will review the case immediately.

The study will be immediately suspended and no additional BVD-523 doses administered pending review and discussion of all appropriate study data by the SMC if 1 or more patients at any dose level develop any of the following adverse events deemed to be possibly, probably, or definitely related to BVD-523 by the Investigator and/or Medical Monitor, based upon close temporal relationship or other factors:

- Death;
- Anaphylaxis (angioedema, hypotension, shock, bronchospasm, hypoxia, or respiratory distress).

The study will not be restarted until all parties have agreed to the course of action to be taken and the IRB/EC has been notified.

3.2 SCHEDULE OF STUDY ASSESSMENTS

Table 3.1. Table of Study Assessments

The schedule of study assessments and procedures for patients in both Part I and Part II of the study is shown below:

	Cycle 1 Day 1 through 21				Cycle 2 Day 22 through 42			Cycle 3-X 21 day cycles, visit on 1st day of cycle	
Visit	1 Screening	2 Baseline	3 Tx	4 Tx	5 Tx	6 Tx	7 Tx	8-X Tx	Final Study Visit/ Early Discontinuation
Visit Day	-14 to -1	1 ± 0	8 ± 1	15 ± 1	22 ± 1	29 ± 1	36 ± 1	43 ± 1	
Informed consent*	X								
Inclusion/exclusion criteria	X	X							
Medical history ¹	X ⁹	X	X	X	X	X	X	X	X
Concurrent medications	X	X	X	X	X	X	X	X	X
Demography	X								
Measure height (cm)	X								
Measure weight (kg)	X	X			X			X	X
Physical examination	X	X	X	X	X	X	X	X	X
ECOG	X	X	X	X	X	X	X	X	X
Vital signs	X	X	X	X	X	X	X	X	X
Ophthalmology exam ²	X								X
Pregnancy test ^{3,4}	X	X ³			X ⁴			X ⁴	X ⁴
Study drug dispensed		X	X	X	X	X	X	X	
Study drug administration ⁵		X	X	X	X	X	X	X	
Pharmacokinetic samples ^{6,7}		X ⁷		X ⁶	X ⁶				
Pharmacodynamic samples ^{6,7,8}		X ⁷		X ⁶					
Tumor measurements ⁹	X							X	X
Clinical lab tests ¹⁰	X	X	X	X	X	X	X	X	X
Electrocardiogram (ECG) ¹¹	X		X						
Holter monitoring ¹²		X		X					
Adverse events (AEs)		X	X	X	X	X	X	X	X
Compliance by pill count			X	X	X	X	X	X	X
Obtain unused drug			X	X	X	X	X	X	X
ECHO cardiogram or MUGA	X								

Table footnotes:

*Note: informed consent may be obtained up to -28 days to allow flexibility in scheduling of the screening procedures.

1 Full medical history at screening, review/update of history only at subsequent visits.

2 Ophthalmological examinations will be performed by an ophthalmologist at screening, at End of Treatment and if clinically indicated.

3 ONLY if the screening serum pregnancy test was performed more than 1 day previously.

4 After screening and baseline, urine pregnancy test which if positive, confirm with serum test.

5 Study drug to be taken twice daily, first dose in clinic on days when PK sampling occurs i.e. Cycle 1 on Visit 2 (Day 1), Visit 4 (Day 15) and morning dose of Cycle 2 on Visit 5, remaining doses on all other days to be self-administered by patient.

6 In Part 1 PK and pharmacodynamic blood samples plus PK urine samples will be taken concurrently on Day 1 and Day 15 along with QTc extractions from the Holter monitoring. PK blood samples will be collected prior to first dose and at 0.5 hours, 1 hour (both ± 5 minutes), 2 hours, 4 hours, 6 hours, 8 hours (all ± 10 minutes), and 12 hours (± 2 hours) post first dose. Blood samples for pharmacodynamic assessment will be collected pre-dose and 4 hours post-dose (± 10 minutes). PK urine samples will be collected prior to first dose and for the 1–6-hour and 6–12 ± 2 -hour time periods post first dose on Day 1 and Day 15. On Day 22, PK and pharmacodynamic samples will be collected prior to the first dose of that day. In Part 2, urine PK will not be performed and blood PK, blood pharmacodynamic, and Holter monitoring will be performed until the sponsor determines they will be discontinued based on accumulated patient experience.

7 PK and pharmacodynamic blood and urine samples are required, and paired tumor tissue and blood samples are to be obtained at baseline where feasible. Tumor genotyping by DNA analysis may be performed to identify somatic alteration. Additional tissue or plasma DNA samples for analysis may also be obtained from selected patients prior to first dose, at steady-state during treatment and/or after disease progression.

8 In Part 2, pharmacodynamic samples only need to be taken if the patient has consented to the optional research tests involving collection of tumor tissue.

9 Tumor assessments will be made by CT/MRI/Physical Exam prior to dose initiation if the patient does not have a recent CT/MRI/Physical Exam on record within 28 days before start of treatment (Visit 2), at the 1st protocol-specified tumor measurement evaluation at the end of Cycle 2 and then every 2-3 cycles, and at End of Treatment if the previous CT/MRI/Physical Exam was conducted 21 or more days earlier. The same imaging modality used for an individual patient (i.e., CT or MRI) at Screening should be maintained throughout the study.

10 Chemistry (to include calcium and inorganic phosphorus), hematology and urinalysis. After Cycle 2, clinical chemistry (to include calcium and inorganic phosphorus), hematology and urinalysis may be performed once per cycle or more frequently at the investigator's discretion.

11 Patients with a normal ECG in Cycle 1 need not have repeat ECGs in subsequent cycles.

12 Holter monitoring for 12 \pm 2 hours during PK sampling.

4 SAMPLE SIZE CONSIDERATIONS

For this Phase 1 dose escalation study, no formal sample size calculations have been performed; the sample size reflects practical considerations.

Approximately 40 patients will be treated in Part 1 of this study (dose-escalation phase) to establish DLT, MTD, and the RP2D.

After the completion of Part 1 of this study, up to 105 additional patients with certain cancer types and/or characterized genetic alterations and/or MAPK pathway activation will be treated with the RP2D (which may be the same or lower than the MTD) to determine if BVD-523 is effective as a single agent therapy. The purpose of the second phase of this first in human research is to merely document that there is some evidence of a response (complete response or partial response per RECIST v 1.1).

5 ANALYSIS POPULATIONS

Five analysis populations will be used to analyze the study data. Below are details of each analysis population:

5.1 SAFETY

The Safety Population consists of all patients receiving at least one dose of study medication.

This population will be used to summarize demographics and baseline characteristics, previous and concomitant medication/therapies, treatment exposure and all safety endpoints including AE, physical examination (PE), ophthalmology examination, clinical laboratory tests (chemistry, hematology, and urinalysis), serum/urine pregnancy test, ECG, Holter monitoring, and vital signs (VS).

5.2 MODIFIED INTENT-TO-TREAT

The modified Intent-To-Treat (mITT) Population is defined as all patients receiving at least one dose of study medication. Subject demographics, disposition, and analysis population summaries will be tabulated using the mITT population.

5.3 PER-PROTOCOL

The Per Protocol population consists of all patients from the modified ITT Population who have completed the first protocol-specified tumor measurement evaluation (except for study drug-related AE) without major protocol violations. All protocol deviations will be reported, but prior to generating TFLs for either Part 1 or Part 2, the list of protocol deviations will be reviewed and each classified as either major or minor. This population will be used to summarize clinical effects on tumor response using RECIST version 1.1 criteria. Analyses based on the PP population will be exploratory.

5.4 PHARMACOKINETIC

The Pharmacokinetic (PK) Population is comprised of all patients who receive at least 1 dose of study drug and have sufficient and valid PK samples to estimate PK parameters (C_{max} , t_{max} ,

AUC_{0-12} , AUC_{0-last} , λ_z , $t_{1/2}$) for Day 1 and/or Day 15. In Part 2, urine PK samples were not collected so urine PK analyses will only be presented for Part 1 subjects.

Pharmacokinetic summaries will be based on the PK population (refer to Section 11.1 of this SAP).

5.5 PHARMACODYNAMIC

The Pharmacodynamics (PD) Population is defined as patients in the Safety Population who provide at least one pharmacodynamic measurement from fluid and/or tumor samples for Day 1 or Day 15, relative to pre-treatment levels.

All pharmacodynamics data will be analyzed based on the pharmacodynamics population.

6 CONSIDERATIONS FOR DATA ANALYSIS

6.1 PROGRAMMING ENVIRONMENT

All analyses will be conducted using SAS[®] version 9.2 or higher.

6.2 STRATA AND COVARIATES

Not applicable.

6.3 SUBGROUPS

The only planned subgroup analyses are the seven patient subgroups from Part 2 (see Section 3.1 of this SAP).

6.4 MULTIPLE COMPARISONS AND MULTIPLICITY

There are no planned adjustments for multiplicity.

6.5 SIGNIFICANCE LEVEL

Unless otherwise noted, all statistical analyses will be conducted using the significance level (α) of 0.05 and utilize two-sided testing. However, no inferential testing is prospectively planned for the current study data.

6.6 STATISTICAL NOTATION AND METHODOLOGY

Unless stated otherwise, the term “descriptive statistics” refers to the number of patients (n), mean, median, standard deviation (STD), minimum (Min), and maximum (Max) for continuous data and frequencies and percentages for categorical data. Min and Max values will be presented using the precision of the original value, means and medians will be rounded to 1 decimal place greater than the precision of the original value, and STDs will be rounded to 2 decimal places greater than the precision of the original value. Percentages will be rounded to the nearest whole number. For percentage values that are less than 1% but greater than 0%, they will be presented as “< 1%”. Similarly, “> 99%” will be used to display percentages that are greater than 99% but less than 100%. P-values will be presented with 3 decimal places and values less than 0.001 will be presented as < 0.001.

All data collected during the study will be included in data listings and will be displayed and sorted by study part, dose level, cohort/treatment group, patient number and then by date/time (including visit, cycle, and day), if any, for each patient number, unless otherwise noted.

7 DATA HANDLING METHODS

7.1 MISSING DATA

7.1.1 Date Values

In cases of incomplete dates (e.g., pertaining to AE, concomitant medication, medical history, etc.), the missing component(s) will be assumed as the most conservative value(s) possible. For example, if the start date has a missing day value, the first day of the month will be imputed for study day computations (i.e., treatment-emergent status, etc.). If day is missing for an end date, the last day of the month will be imputed. Similar logic will be assumed for missing month and year components.

Date imputation will only be used for computational purposes e.g., treatment-emergent status, etc. Actual data values as they appear in the original CRFs will be shown in the data listings.

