7.2 VISIT WINDOWS

All study data will be presented at the nominal visit obtained from the eCRFs, if available. Study day is defined as (date of visit – date of treatment initiation + 1). That is, study day 1 indicates the date of treatment initiation. In the case of early termination visit, date of the visit will be used to calculate the nominal visit for the analysis.

If there are two or more assessments within a nominal visit, then the assessment that is closest to the scheduled time point/target day will be used in the analysis. If there is more than one closest value, then the evaluation occurring after the target day and prior to the date of last dose will be used in the analysis.

All values will be included in the data listings.

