8.3 PRIOR AND CONCOMITANT MEDICATIONS

Medications will be coded according to the World Health Organization Drug Dictionary (WHO Drug, March 1, 2013). Summary of all medications will then be using the WHO Drug ATC classification and preferred term.

All medications taken, except for BVD-523, will be classified into prior or concomitant medications. A prior medication is defined as any medication taken within 28 days prior to the initiation of BVD-523 irrespective of whether it is continued into the study. A concomitant medication is defined as any medication taken after the initiation of BVD-523 and up to 30 calendar days after the last administration of BVD-523. If a medication falls into both prior and concomitant time phase then it will be presented in both time phases. All medications, except for BVD-523, will be summarized by WHO Drug ATC classification and preferred term with regards to treatment groups for each study part and time phase.

At each level (WHO Drug ATC classification and Preferred Term) of summarization, a subject will be counted only once per drug class or preferred term. For example, if a subject reports multiple concomitant medications with the same drug class, then that drug class will only be incremented by one. Similarly, if a subject reports multiple concomitant medications with the same preferred term, then that preferred term will only be incremented by one. Whether medications are taken for AEs or not will also be provided. The medication with indication equals to the AE verbatim which also has “Concomitant Medications” as the response to the question of “Any Treatment Required?” will be deemed as the medication taken for the AE. Medications taken for AEs will be tabulated by WHO Drug ATC classification and preferred term with regards to treatment groups for each study part.

Subject listing of medications will also be presented by time phase.

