10.2 ADVERSE EVENTS

An adverse event is defined as any untoward medical occurrence in a patient administered a medicinal product that does not necessarily have a causal relationship with this treatment. This includes an exacerbation of pre-existing conditions or events, inter-current illnesses, drug interaction, or the significant worsening of the indication under investigation that is not recorded elsewhere in the eCRF under specific efficacy assessments. The reporting period of an AE begins from the time that the patient provides informed consent through and including 30 calendar days after the last administration of BVD-523 (or at the time when a patient begins a new anti-cancer therapy). Anticipated fluctuations of pre-existing conditions, including the disease under study that does not represent a clinically significant exacerbation or worsening, need not be considered AEs.

The severity of an AE will be graded according to the National Cancer Institute (NCI) Common Terminology Criteria for Adverse Events (CTCAE), version 4 with values of Grade 1 to Grade 5 (increased in severity). For AEs not covered by NCI CTCAE, the severity will be characterized as “mild,” “moderate,” or “severe” according to the following definitions:

- Mild (equivalent to Grade 1) events are usually transient and do not interfere with the patient’s daily activities.
- Moderate (equivalent to Grade 2) events introduce a low level of inconvenience or concern to the patient and may interfere with daily activities.
- Severe (equivalent to Grade 3) events interrupt the patient’s usual daily activities.

All AE relationship to the study drug, BVD-523, are classified as “unrelated,” “possibly related,” or “related.”

AE Coding

Any AE including SAE in verbatim term will be coded in accordance with the Medical Dictionary for Regulatory Activities (MedDRA®) dictionary version 16.0 to a system organ class (SOC) and preferred term (PT) within each SOC. Analysis of AEs will then be performed using SOCs and PTs.

Dose Limiting Toxicities, Maximum Tolerated Dose, and Recommended Phase 2 Dose

As specified in Section 2.1.1, a DLT for Part 2 is defined (per definition in protocol amendment 7) as a **BVD-523 related toxicity in the first 21 days** of treatment that results in:

- \geq Grade 4 hematologic toxicity for > 1 day;
- Grade 3 hematologic toxicity with complications e.g., thrombocytopenia with bleeding;

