- \geq Grade 3 non-hematologic toxicity, except untreated nausea, vomiting, constipation, pain, and rash (these become DLTs if the AE persists despite adequate treatment), a doubling of AST/ALT in patients with grade 2 ALT/AST at baseline;
- A treatment interruption exceeding 5 days (or an interruption exceeding 7 days for rash, despite adequate treatment) in Cycle 1 (or inability to begin Cycle 2 for > 7 days) due to BVD-523-related toxicity³.

As specified in Section 2.1.1, the MTD is defined as the highest dose level at which $\leq 33\%$ of patients experience BVD-523 related DLTs in the first 21 days of treatment. The RP2D may be as high as the MTD and will be determined in discussion with the Clinical Investigators, the Medical Monitor, and the Sponsor. Observations related to pharmacokinetics (PK), pharmacodynamics (PD), and any cumulative toxicity observed after multiple cycles may be included in the rationale supporting the RP2D. Pharmacokinetic, pharmacodynamics, and/or Holter measurements may be suspended pending review of accumulated patient experience.

Treatment Emergent Adverse Event

A treatment emergent adverse event (TEAE) is any AE temporally associated with the use of BVD-523 (from BVD-523 initiation until 30 calendar days after the last administration of BVD-523), whether or not considered related to the study drug. If the onset of an AE is missing and the AE resolution date is either after the initial BVD-523 dose date or missing, then the AE will be considered treatment emergent.

AE Summaries

A subject who reported multiple AEs that map to a common PT or SOC is counted only once for that PT or SOC at the highest severity reported and at the greatest relationship to study drug.

The number and percentage of subjects who experienced at least one AE will be tabulated by SOC and PT with respect to dose level/treatment group for each study part. The same tabulation will also be applied to any SAE, any AE leading to premature discontinuation from the study, treatment emergent AEs and treatment-emergent SAEs.

³ For Amendments 1 and 2: A treatment interruption exceeding 3 days in Cycle 1 due to drug-related toxicity (or inability to begin Cycle 2 for > 7 days) due to drug-related toxicity.

For Amendment 3: A treatment interruption exceeding 5 days in Cycle 1 due to drug-related toxicity (or inability to begin Cycle 2 for > 7 days due to drug-related AE)

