Part I - Table 14.3.1.9	Adverse Events by Severity	Safety Population
Part I - Table 14.3.2.1	Treatment Emergent Adverse Events	Safety Population
Part I - Figure 14.3.2.1	Bar Graph of Treatment Emergent Adverse Events	Safety Population
Part I - Table 14.3.2.2	Serious Treatment Emergent Adverse Events	Safety Population

Part I: Death Narratives

Part I: Laboratory Results

Part I - Table 14.3.4.1	Laboratory Evaluations – Hematology	Safety Population
Part I - Table 14.3.4.2	Laboratory Evaluations – Clinical Chemistry	Safety Population
Part I - Table 14.3.4.3	Laboratory Evaluations – Urinalysis	Safety Population

Part I: Physical Examination Results

Part I - Table 14.3.5.1	Physical Examinations	Safety Population
Part I - Table 14.3.5.2	ECOG Performance Status	Safety Population
Part I - Table 14.3.5.3	Electrocardiograms	Safety Population
Part I - Table 14.3.5.4	Categorized Electrocardiograms	Safety Population
Part I - Table 14.3.5.5	Ophthalmology Examinations	Safety Population
Part I - Table 14.3.5.6	Vital Signs	Safety Population

Part I: Pharmacokinetics

Part I - Table 14.4.1	Pharmacokinetic Parameters Calculated from Blood Samples	PK Population
Part I - Table 14.4.2	Pharmacokinetic Parameters Calculated from Urine Samples	PK Population

Part I: Pharmacodynamics

Part I - Table 14.5.1	Fluid Pharmacodynamics	Pharmacokinetics Population
-----------------------	------------------------	-----------------------------

Part I: Tumor Genotyping

Part I - Table 14.6.1	Tumor Genetic Information	PP Population
-----------------------	---------------------------	---------------

Part II

Part II: Study Population

Part II - Table 14.1.1.1	Subject Disposition	mITT Population
Part II - Table 14.1.1.2	Analysis Population	mITT Population
Part II - Table 14.1.2	Protocol Deviations	mITT Population
Part II - Table 14.1.3.1	Demographic and Baseline Characteristics	Safety Population
Part II - Table 14.1.3.2	Demographic and Baseline Characteristics	mITT Population
Part II - Table 14.1.4.1	Prior Medications	Safety Population
Part II - Table 14.1.4.2	Concomitant Medications	Safety Population

Part II - Table 14.1.4.3	Concomitant Medication Taken for Adverse Events	Safety Population
Part II - Table 14.1.5.1	Treatment Compliance	Safety Population
Part II - Table 14.1.5.2	Exposure to Study Drug	Safety Population
Part II - Table 14.1.6	Pregnancy Test Results	Safety Population
Part II: Efficacy		
Part II - Table 14.2.1	Target Lesion Response per RECIST 1.1	PP Population

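### A missing AE start day becomes the first of the month with no floor at first dose, so on-treatment events in the first-dose month drop out of the TEAE tables

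*SAP*

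**What the plan says.** SAP 7.1.1 sets the principle that missing parts of a date take the most conservative value. It then gives the working rule: "if the start date has a missing day value, the first day of the month will be imputed for study day computations". Treatment-emergent status is named there as a purpose of the imputation. A missing end day goes to the last of the month. For larger gaps, "Similar logic will be assumed for missing month and year components".

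SAP 7.2 fixes the time scale: "study day 1 indicates the date of treatment initiation". SAP 10.2 defines a TEAE as an event in the window "from BVD-523 initiation until 30 calendar days after the last administration of BVD-523". It has one fallback, for the case "If the onset of an AE is missing and the AE resolution date is either after the initial BVD-523 dose date or missing"; such an event counts as treatment-emergent. The fallback does not mention partial dates.

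Events are collected before treatment as well. SAP 10.2 states: "The reporting period of an AE begins from the time that the patient provides informed consent". A true pre-treatment category therefore exists, and the flag has to separate the two groups.

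**The concern.** For a safety table, the cautious choice is to count a doubtful event. The first of the month does this at the end of the TEAE window, where it pulls an event of unknown day back inside. At the start of the window it does the opposite: it moves the event to a date before first dose and so out of the table. The worked example in SAP 7.1.1 thus runs against the principle it illustrates, in the month when early toxicity appears.

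The outputs at stake, in both parts, are Table 14.3.2.1 and Figure 14.3.2.1 (TEAEs) and Table 14.3.2.2 (treatment-emergent SAEs, titled "Serious Treatment Emergent Adverse Events" in Part I). Their error goes one way: on-treatment events are removed and none are added.

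The rule also orders the evidence oddly. Suppose the end date is after first dose or missing. An event with no onset date at all counts as treatment-emergent under SAP 10.2, while an event known to have started in the first-dose month does not.

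**Working it through.** The plan states no figure on this point, so there is none to reproduce. The check applies the SAP rule to every possible first-dose date.

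**Inputs.** Imputation to the first of the month (SAP 7.1.1); TEAE if the imputed onset is on or after first dose (SAP 10.2); study day = date - first-dose date + 1 (SAP 7.2); Cycle 1 of 21 days. Assumptions: first-dose dates and true onsets are uniform.

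**Single patient.** With first dose on day d and onset in the same month, imputed study day = 1 - d + 1 = 2 - d. This is before treatment for every d of 2 or more. For d = 15 it is -13.

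**30-day month, Cycle 1 onsets.** The number of Cycle 1 days in the first-dose month is min(21, 31 - d).
- d = 1 to 10: 10 × 21 = 210.
- d = 11 to 30: 20 + 19 + ... + 1 = 210.
- Total 420 of 30 × 21 = 630. First dose on the 1st is harmless, so subtract 21: **399/630 = 63.3%**.

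**365-day calendar, Cycle 1 onsets.** The same count gives 420 for a 31-day month, 399 for a 30-day month and 357 for February: 7 × 420 + 4 × 399 + 357 = 4,893. Out of 365 × 21 = 7,665, this is **63.8%**.

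**Onsets in the first 7 days.** The counts per month are 189, 182 and 168: 7 × 189 + 4 × 182 + 168 = 2,219. Out of 365 × 7 = 2,555, this is **86.8%**.

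**Month missing too, read as January.** Onsets in the first-dose year number 7,665 - (20 + 19 + ... + 1) = 7,455. Less 21 for a first dose on 1 January, this leaves 7,434/7,665 = **97.0%**.

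**With a floor at first dose.** For a missing day, 0/7,665 on-treatment onsets are imputed to before first dose.

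**Price of the floor.** AEs that truly began before first dose are classified correctly now. With the floor, a screening event of unknown day in the first-dose month becomes a TEAE, unless its end date shows otherwise. In a 30-day month, the number of the preceding w days that fall in that month is min(w, d - 1).
- w = 7: (0 + 1 + ... + 6) + 23 × 7 = 182 of 210 = 86.7%.
- w = 14: (0 + 1 + ... + 13) + 16 × 14 = 315 of 420 = **75.0%**.
- w = 28: (0 + 1 + ... + 27) + 2 × 28 = 434 of 840 = **51.7%**.

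These are upper limits, before the end-date exception.

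**The case against.** **Other rules may rescue the events.** SAP 7.1.1 leads with the conservative principle. SAP 7.3 leaves endpoint-specific derivations to the endpoint's own section, and the fallback in SAP 10.2 could be read to cover partial onsets. SAP 7.1.2 also allows visit dates to be imputed to place AEs in a study phase. None of this settles the matter. The fallback is worded for a missing onset, and SAP 7.1.1 has already completed a partial one. SAP 7.1.2 speaks only of visit dates and sets no floor. A programmer will code the explicit example.

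**Few dates will be partial.** Cycle 1 visits are about a week apart (Protocol 5.2), the eCRF has completeness checks (Protocol 11.8), and SAE reports must carry onset date and time (Protocol 9.8). This stands. The percentages are shares of an unknown and probably small number. The 97% is the least likely case, and it rests on reading the similar-logic sentence as January.

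**No primary output changes.** This also stands. Nothing ties DLT counts to the TEAE flag. The all-AE, SAE, relationship and severity tables and the raw-date listings keep these events, and no inferential testing is planned (SAP 6.5).

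**The fix swaps one error for another.** In part it does. For screening events in the 7 days before first dose, the relabelled share can reach 87%, about the same as the share of first-week events now lost. But over-counting TEAEs is the direction SAP 7.1.1 says it wants.

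**Conclusion.** The concern holds. Followed as written, SAP 7.1.1 and 10.2 class every on-treatment AE of unknown day in the first-dose month as pre-treatment, unless first dose fell on the 1st. Under uniform first-dose dates and onsets, that is about 64% of Cycle 1 AEs with a missing start day and 87% of those from the first 7 days. The effect on the actual TEAE counts cannot be sized, because the documents do not say how many start dates are incomplete. The defect is confined to the TEAE displays and does not touch the dose-finding endpoints. It should still be corrected, because the plan contradicts its own aim and always under-counts early events.

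**What to change.** In SAP 7.1.1, add a rule for AE start dates only. If the known month and year match those of first dose (or the year alone, when the month is missing), impute the first-dose date, unless the known end date is before first dose. Otherwise impute the first of the month, or 1 January. State that a partial end date is completed as SAP 7.1.1 already provides before this test is applied. In SAP 10.2, state that partial onsets follow this rule and that the existing fallback is for onsets missing altogether.

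Leave medication start dates alone. SAP 8.3 already deals with a drug that spans first dose: "If a medication falls into both prior and concomitant time phase then it will be presented in both time phases".

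The cost is a short addition to the SAP text and about a line of code, plus the relabelled screening events described above. SAP 15 records a Part 1 SAP signed in March 2015. If the Part 1 tables were produced under the same rule, which the documents do not show, either rerun the Part 1 TEAE displays or note the difference between parts in the report.
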